| 12.1.2 Parameters for the prior distribution – Scenario 1 | 23 |
| 12.1.3 Parameters for the prior distribution – Scenario 2 | 23 |
| 12.1.4 Parameters for the prior distribution – Scenario 3 | 23 |
| 12.1.5 Parameters for the prior distribution – Scenario 4 | 24 |
| 12.2 Patient demographic and other baseline characteristics | 24 |
| 12.3 Analysis of other variables | 24-25 |
| 13. Timeline estimate | 25 |
| 14. Biomarker Assessments | 25-26 |
| 15. References | 26 |
| Appendix 1: Cognitive/Functional Assessments | 227 |
| Appendix 2: Patient Reported Surveys | 27 |

List of Tables

| | |
|---|-------|
| Table: Recommended data collection schedule | 16-17 |
|---|-------|

LIST OF ABBREVIATIONS

| | |
|------|---|
| CSF | cerebrospinal fluid |
| CIU | core imaging unit |
| CCU | core clinical unit |
| EDSS | expanded disability status scale |
| EOS | end of study |
| IRB | institutional review board |
| MRI | magnetic resonance imaging |
| MS | multiple sclerosis |
| MSFC | multiple sclerosis functional composite |
| PI | principal investigator |
| PRO | patient reported outcomes |
| RIS | radiologically isolated syndrome |

PROTOCOL SYNOPSIS

Title of study: Multi-center, randomized, double-blinded assessment of Tecfidera® in extending the time to a first attack in radiologically isolated syndrome (RIS) (ARISE)

Purpose: To prospectively study the efficacy of Tecfidera in extending the time to a seminal acute or progressive demyelinating event in a cohort of U.S. RIS subjects.

Rationale: RIS subjects are frequently exposed to disease modifying therapies despite the lack of scientific literature supporting the use of such treatments. Earlier treatment intervention may extend the time to the first acute or progressive clinical event resulting from CNS demyelination and reduce new radiological activity. In addition, early treatment may result in more profound effects on reducing disability progression long-term.

Primary outcome: The primary outcome measure for this trial is the time to the first acute or progressive neurological event resulting from CNS demyelination from randomization into the trial.

Population: This study will include RIS subjects from the U.S. who fulfill 2009 RIS Criteria¹.

Inclusion/Exclusion criteria:

Inclusion criteria

1. Males and females 18 years of age and older meeting 2009 RIS criteria¹
2. Identified RIS cases with the initial MRI demonstrating anomalies suggestive of demyelinating disease dated \geq 2009
3. Incidental anomalies identified on MRI of the brain or spinal cord with the primary reason for the acquired MRI resulting from an evaluation unrelated to multiple sclerosis
4. CNS white matter anomalies meeting the following MRI criteria:
 - a. Ovoid, well-circumscribed, and homogeneous foci with or without involvement of the corpus callosum
 - b. T2-hyperintensities measuring $> 3\text{mm}^2$ and fulfilling 3 of 4 Barkhof-Tintoré criteria for dissemination in space
 - c. CNS anomalies not consistent with a vascular pattern
 - d. Qualitative determination that CNS anomalies have a characteristic appearance of demyelinating lesions
5. MRI anomalies do not account for clinically apparent neurological impairments in patients

Exclusion criteria

1. Women who are pregnant or nursing
2. Incomplete medical history or radiological data
3. History of remitting clinical symptoms consistent with multiple sclerosis lasting > 24 hours prior to CNS imaging revealing anomalies suggestive of multiple sclerosis
4. History of paroxysmal symptoms associated with MS (i.e. Lhermitte's or Uhthoff's phenomena)
5. CNS MRI anomalies are better accounted for by another disease process
6. The subject is unwilling or unable to comply with the requirements of the study protocol

7. Exposure to a disease modifying therapy for multiple sclerosis/RIS within the past 3 months
8. Exposure to high-dose glucocorticosteroid treatment within the past 30 days
9. Participation in other clinical trials involving treatment with a disease-modifying agent

Study design: Prospective, randomized, double-blinded, multi-center

Key data collection:

1. Clinical data
2. Radiologic data
3. Cognitive/Functional Assessments (EDSS, MSFC-expanded)
4. Patient reported surveys
5. Biological samples (CSF, serum DNA and RNA) for future mechanistic studies

Data analysis:

Primary analysis:

- We will evaluate the time from randomization to the first demyelinating event (acute or development of an initial symptom resulting in a progressive clinical course) utilizing Kaplan-Meier survival analyses. Log-rank tests will be used to compare survival data between groups at univariate analysis.

Secondary analyses:

- Multivariate Bayesian Cox regression models will be created to assess the independent predictive value of demographic characteristics (i.e. sex, ethnicity, age at the time of RIS diagnosis), clinical data (i.e. MS family history, occult neurological examination findings, environmental exposure data, cognitive performance, PRO, CSF profiles, etc.), and imaging data (i.e. number of brain MRI lesions, the presence of gadolinium enhancing lesions, geographical distribution of lesions, involvement of the spinal cord, brain atrophy, etc.) on the time to the first symptomatic event.
- The association of each covariate with time to the first clinical symptom will be quantified by hazard ratios (HR) along with their 95% confidence intervals (CI). Assessments to determine differences between centers will also be performed with statistical adjustments planned for subsequent analyses depending upon the obtained results.
- MRI outcomes (proportion of subjects with gadolinium enhancement and new radiologic activity).

ABOUT THIS STUDY

A strategic research alliance was formed between the Radiologically Isolated Syndrome Consortium (RISC) and Biogen to explore this important initiative of investigating the impact of early treatment intervention in subjects who possess the first visible manifestation of multiple sclerosis. This collaboration enabled the development and effective execution of an innovative approach in demyelinating disease more quickly and strategically. The current home of RISC, the University of Texas Southwestern Medical Center at Dallas (Texas, U.S.A.) is proud to serve as the study sponsor for this novel research study.

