5.3 Study Design

This is a multi-center, randomized, double-blinded study in which approximately 90 RIS subjects (refer to section 12 for sample size justification) will be treated with either Tecfidera or placebo (1:1 randomization) for 3 years or until End of Study (EOS) which is March 31, 2021. The primary outcome measure is the time to the first acute or progressive neurological event resulting from CNS demyelination. The secondary outcome measures include the number of new or enlarging T2 lesions, and the change in the number of contrast enhancing lesions, and T2-lesion and brain volumes. Study participants, along with the treating and examining physicians, will be blinded to treatment assignment. Central Clinical and Imaging Units will screen all potential study subjects for inclusion/exclusion criteria. We expect to enroll all RIS subjects within the U.S.

Following informed consent and verification of entry criteria by the core units, study participants will be randomized 1:1 to either Tecfidera (120mg by mouth twice daily for 7 days with dose escalation to 240mg by mouth twice daily) or placebo. Clinical follow-up by the treating physician, as defined within this protocol, will occur at weeks **0, 48, 96, 144 and/or EOS** and during or immediately following clinical exacerbations. (please refer to Study Schematic). During clinical visits comprehensive medical history data, safety labs, and optional biological samples will be obtained by the treating physician.

Patients will be scheduled for safety screenings (CBC & CMP) at weeks **12, 24, 72, 120**; at which time they will be seen by research coordinator or research nurse.

In addition to the face-to-face visits described above, study participants will be contacted over the telephone at weeks **4, 8, 36, 60, 84, 108, and 132** to assess for medical or treatment difficulties in addition to study medication compliance.

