12.1 Power calculation

A Bayesian approach has been used to calculate the sample size. The Bayesian approach is based on combining a prior distribution for the treatment effect with the result of the trial (which represents here the likelihood). The prior distribution for the effect of Tecfidera vs. placebo was built using the data from DEFINE and CONFIRM trials in RRMS.

12.1.1 Parameter estimates for the rate of events in the RIS cohort in a Bayesian framework

The parameters for the expected treatment effect of a 50% reduction in the risk of the first clinical event are $HR=0.50$ (i.e. $\log HR=-0.69$). A SD for $\log HR$ is set to 2.2 to get a power of 80% to detect a 50% reduction in the hazard of events with 80 patients per arm (original design). This base scenario is set in order to use the same assumptions done as for the original calculations.

Several scenarios were considered to allow a sensitivity analysis for the power calculations.

12.1.2 Parameters for the prior distribution – Scenario 1

The 2 arms treated with Tecfidera are pooled together (i.e. same efficacy)
Patients from DEFINE and CONFIRM are classified as “early RRMS” if they had:

- No previous treatment
- Less than 5 years from disease onset
- EDSS≤1.5

| | Placebo | Tecfidera | Total |
|-------|---------|-----------|-------|
| RRMS | 703 | 1372 | 2075 |
| Early | 68 | 157 | 225 |
| Total | 771 | 1529 | 2300 |

225 patients are classified as Early in the 2 trials merged.

Treatment effect in the “Early” group ($HR=0.24$, risk reduction=76%) $\log HR=-1.45$; $SE=0.31$.
Treatment effect in the rest of RRMS ($HR=0.59$, risk reduction 41%)

The parameters of the prior distribution, according to the Tecfidera effect in early RRMS in the DEFINE+CONFIRM studies, are: mean=-1.45, SD=0.31.

12.1.3 Parameters for the prior distribution – Scenario 2

The 2 arms treated with Tecfidera are pooled together (i.e. same efficacy)
We take the Tecfidera effect form the merged trials: $HR=0.58$, risk reduction=42%; $\log HR=-0.548$; $SE=0.073$.

The parameters of the prior distribution, according to the Tecfidera effect all the patients included in the DEFINE+CONFIRM studies, are: mean=-0.548, SD=0.073.

12.1.4 Parameters for the prior distribution – Scenario 3

The 2 arms treated with Tecfidera are pooled together (i.e. same efficacy)
We take the Tecfidera effect from the merged trials: HR=0.58, risk reduction=42%

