We assume the treatment effect on the RIS cohort to be reduced by 20% since there is a portion of RIS that are not subclinical MS.

HR=0.58*1.20 =0.70

logHR=-0.36

mean=-0.36, SD=0.073.

12.1.5 Parameters for the prior distribution – Scenario 4

The 2 arms treated with Tecfidera are pooled together (i.e. same efficacy)
We take the Tecfidera effect from the merged trials: HR=0.58, risk reduction=42%; SE=0.073

We assume the treatment effect on the RIS cohort to be reduced by 30% since there is a portion of RIS that are not subclinical MS.

HR=0.58*1.30 =0.75; logHR=-0.282; mean=-0.282, SD=0.073

We report here the different power estimates for a sample size of 80 RIS patients (40 per arm) according to the 4 scenarios and 4 different assumptions on SD (representing those observed multiplied by 2, 3, 4 and 5).

| | Prior HR | Parameters for the prior | SD | | | |
|--|-----------------|----------------------------------|------|--------|--------|-----|
| | | | x2 | x3 | x4 | x5 |
| Scenario 1 (early RRMS, subgroup of the trials) | HR=0.235 | Prior mu=-1.45, SD=0.31 | 86% | 70% | 63% | 9% |
| Scenario 2 (all RRMS in the trials) | HR=0.58 | Prior mu= -0.548, SD=0.07 | 100% | 99.60% | 91.30% | 80% |
| Scenario 3 (all RRMS with an effect diluted by 20%) | HR=0.70 | Prior mu= -0.362, SD=0.07 | 99% | 86% | 70% | 61% |
| Scenario 4 (all RRMS with an effect diluted by 30%) | HR=0.75 | Prior mu= -0.282, SD=0.07 | 96% | 67% | 56% | 49% |

Overall, the power analysis shows that the projected sample size of 80 patients should result in adequate power for the majority of scenarios considered.

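### The sample size is justified by a Bayesian rule that borrows RRMS data, but the stated primary test is a log-rank test with about 51% power at 80 patients and 56% at 90

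*Protocol*

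**What the plan says.** - **Primary analysis (synopsis, Data analysis).** Time from randomization to the first demyelinating event is analysed by Kaplan-Meier. The comparison between groups is: "Log-rank tests will be used to compare survival data between groups at univariate analysis". No prior is mentioned.
- **Secondary analyses (synopsis, repeated in 12.3).** Bayesian modelling appears only here, and for covariates: "Multivariate Bayesian Cox regression models will be created to assess the independent predictive value of demographic characteristics".
- **Sample size (12.1).** "The Bayesian approach is based on combining a prior distribution for the treatment effect with the result of the trial". The prior comes from two RRMS trials of Tecfidera.
- **Base case (12.1.1).** The effect is HR 0.50. An SD of 2.2 for the log HR was chosen, and the protocol gives the purpose: "to get a power of 80% to detect a 50% reduction in the hazard of events with 80 patients per arm". That size is described as the original design. The heading reads "Parameter estimates for the rate of events in the RIS cohort in a Bayesian framework", but no event rate or event count follows.
- **Power table and conclusion (12.1.5).** Power is tabulated for 80 patients in total, 40 per arm, under four priors whose SDs are multiplied by 2 to 5. The conclusion is: "Overall, the power analysis shows that the projected sample size of 80 patients should result in adequate power for the majority of scenarios considered".
- **Design (5.3).** About 90 subjects are planned, and section 12 is cited as the justification.

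**The concern.** The power of a design belongs to a specific test. The only primary comparison in this protocol is a log-rank test, which uses the trial's own events and nothing else. The tabulated power comes from a rule that adds outside RRMS evidence to those events. No stated analysis of the primary outcome uses that evidence.

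The number per arm has halved, from 80 to 40 in the table (or about 45 under 5.3), and only the prior makes up the loss. If the log-rank test is what is run, a true halving of the hazard would be missed about half the time. A non-significant result would then be read against a statement of adequate power that was calculated for a different analysis.

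**Working it through.** **Inputs from the protocol.** HR 0.50; SD 2.2; 80% power at 80 per arm (12.1.1). 40 per arm (12.1.5). About 90 patients, 1:1, so 45 per arm (5.3). Prior means and SDs from the table in 12.1.5.

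**Inferred inputs.** Two-sided 5%, and SE of the log HR = 2.2/√(n per arm). The protocol states neither.

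**1. Reproduce the base case.** Power = Φ(|ln HR|/SE − 1.96).
- 80 per arm: SE = 2.2/√80 = 0.246; 0.693/0.246 = 2.818; Φ(0.858) = 80.5% (80.1% with the rounded 0.69). This matches the stated 80%.
- Other readings do not match: one-sided 5% gives 88%; an ordinary two-sample SD gives 51%; SE = 2.2/√160 gives 98%.
- The implied number of events is 4/SE² = 66, which is also what Schoenfeld's formula requires for 80% power at HR 0.50.

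**2. Same inputs at the planned size, no prior.**

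| | SE | Implied events | Power at HR 0.50 |
|---|---|---|---|
| 40 per arm (80) | 0.348 | 33 | 51.3% |
| 45 per arm (90) | 0.328 | 37 | 56.1% |

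The 33 events in 80 patients correspond to about 52% of placebo patients and 1 − √0.48 = 31% of Tecfidera patients: 40 × (0.52 + 0.31) ≈ 33. Simulated log-rank tests with exponential times (20,000 runs) at that placebo risk gave 50.9% and 55.0%.

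**3. Other hazard ratios that the protocol names, 80 / 90 patients.** HR 0.235: 99% / 99%. HR 0.58: 35% / 38%. HR 0.70: 18% / 19%. HR 0.75: 13% / 14%.

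**4. Fewer events (placebo risks are assumptions, HR 0.50).** Events = n per arm × (p + 1 − √(1−p)).

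| Placebo risk | Events, 80 / 90 patients | Power by formula | Power by simulation |
|---|---|---|---|
| 30% | 19 / 21 | 32.0% / 35.3% | 30.6% / 33.7% |
| 20% | 12 / 14 | 22.7% / 25.0% | 21.5% / 23.6% |

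Section 13 allows 18 months between last patient in and last patient out, so the latest enrollees have less than the three years of treatment in 5.3.

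**5. Confirm that the table is prior-based.** Inferred rule: normal prior and normal likelihood with SE 2.2/√40, true HR 0.50, and success if posterior P(HR<1) > 0.975. The prior SD is as printed in the table (0.31 or 0.07), times 2 to 5. The last column is the same rule's false-positive rate at HR = 1.

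| Scenario | Printed power, ×2 / ×3 / ×4 / ×5 (%) | Recomputed (%) | False-positive rate at HR = 1 (%) |
|---|---|---|---|
| 1 | 86 / 70 / 63 / 9 | 86 / 69 / 61 / 58 | 18 / 7 / 4 / 4 |
| 2 | 100 / 99.6 / 91.3 / 80 | 100 / 99 / 90 / 78 | 100 / 70 / 24 / 11 |
| 3 | 99 / 86 / 70 / 61 | 100 / 85 / 68 / 60 | 88 / 17 / 6 / 4 |
| 4 | 96 / 67 / 56 / 49 | 96 / 66 / 55 / 51 | 40 / 6 / 3 / 3 |

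Before rounding, 14 of 16 cells agree within 2 points. The misses are Scenario 4 ×5 (51.2 against 49) and Scenario 1 ×5 (57.7 against 9, probably a misprint). With the SD of 0.073 given in the text of 12.1.3 to 12.1.5, only about half the cells match.

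Eight of the 16 printed cells reach 80%. Under this rule each of those eight has a false-positive rate between about 11% and 100%, so they cannot stand in for a test at 5%.

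**The case against.** **The 51% rests on inferred inputs.** Alpha and the conversion of SD to SE are not in the protocol, and they were chosen because they return 80%. This stands as a condition on the figure. It does not rescue the claim: one-sided 5% gives only 64% and 68% at 80 and 90 patients, and would give 88% rather than 80% for the base case.

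**The protocol does not settle which side governs.** Section 12 has no subsection on the primary analysis, and a separate SAP could make the prior-based analysis primary. That would be another way to remove the conflict. But the synopsis labels the log-rank comparison as primary, so the protocol contradicts itself whatever a later document says.

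**The closing sentence describes the Bayesian exercise, and its scenarios are the four priors.** On that reading all four reach at least 86% at SD ×2, so the cell count alone does not refute it. This is fair in part. Only two of the four reach 80% at ×3 and one of the four at ×4 and ×5. The sentence is also the protocol's only conclusion on power, so it will be read as applying to the primary test.

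**The hazard ratios 0.235 to 0.75 are prior means in the table.** Correct: the figures in step 3 are not row-by-row replacements for the printed cells. Sections 12.1.4 and 12.1.5 do present 0.70 and 0.75 as assumed effects in RIS, so log-rank power at those values is relevant.

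**Several items are small.** The difference between 0.073 and 0.07 and the 9% cell are secondary, and 90 is more than the 80 that section 12 justifies. They are corrections to make in the same edit, not the reason for the concern.

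**Conclusion.** The concern holds. The sample-size justification and the stated primary test do not match, and that follows from the text alone. Log-rank power at HR 0.50 is about 51% with 80 patients and 56% with 90. This is conditional on two-sided 5% (inferred), SE = 2.2/√(n per arm) (inferred), and the event proportion implied by SD 2.2, about 41% overall (33 of 80). The protocol gives no event rate, so that proportion cannot be checked. At the assumed placebo risks of 20% to 30%, power falls to roughly 22% to 35%. About 80 patients per arm would be needed for 80% power on the protocol's own inputs. The claim of adequate power must be corrected because it does not apply to the primary analysis.

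**What to change.** In section 12.1:

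1. State the power of the log-rank test, with alpha, sidedness and the assumed event proportion per arm.
2. Give power at HR 0.50 as conditional on SD 2.2: about 51% at 80 patients (33 events) and 56% at 90 (37 events). Show how it falls with fewer events.
3. Remove the adequacy sentence, or limit it to the analysis it describes.
4. Make 5.3 and section 12 give the same number of patients.
5. If the prior-based analysis is kept, label it supportive. Fix one prior with one SD (0.073 or 0.07), state the decision rule, and report its false-positive rate at HR = 1. If the sponsor instead intends it as primary, the synopsis must say so, with the same details.
6. Check the 9% cell (Scenario 1, SD ×5), which recomputes to about 58%.

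The change is to protocol wording only, with no extra patients or visits. The cost is a less favourable stated power. The edit does not raise the power itself, but it lets a null result be read correctly.

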3.2 Secondary objectives

The secondary objectives of this study include the change in the number of new or enlarging T2 lesions, contrast enhancing lesions, T2-lesion volumes, and brain atrophy at End of Study.

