5. STUDY PROCEDURES

5.1 Hypothesis

We hypothesize that treatment with Tecfidera will i) extend the time to the first acute or progressive demyelinating event by reducing CNS autoimmune inflammation and ii) reduce the development of new MRI lesions within the CNS compared to subjects randomized to placebo.

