5.2 Central Clinical and Imaging Units

To accurately identify subjects with RIS, formal units will be created to review data prior to study entry.

5.2.1 Core Clinical Unit:

A Core Clinical Data Unit, led by [name], will be formed and comprised of a prominent international collaborator and trained MS specialist. This group will evaluate clinical information from both existing and new cases within partnering centers, including results from para-clinical studies (i.e. blood work, CSF, electrophysiological studies, etc.) to ensure that subjects accurately fulfill criteria for study entry. In addition, this group will be responsible for adjudicating all neurological events and post-attack clinical data during the study period. If a discrepancy exists between reviewers following the independent review of submitted cases, [name] will provide a decision on the final classification. The Core Clinical Unit will unify all screening data (including conclusions from the Central Imaging Unit (below)) and will notify participating site PIs when entry criteria are met for potential study participants.

5.2.2 Central Imaging Unit:

A Central Imaging Unit will be formed and will be comprised of a board certified neuro-radiologist and MS specialist with neuro-imaging expertise. The MS specialist will confirm screened cases for study entry. MRI scans from subjects will be independently reviewed by the MS specialist and neuro-radiologist and determinations made if subjects fulfill MRI criteria for RIS. If a discrepancy exists between the two reviewers following the independent review of a case the MS specialist with neuro-imaging expertise will provide a decision on the final classification. The MS specialist with neuro-imaging expertise will also be responsible for

ensuring that a uniform protocol (“Dummy scans”) is implemented at specified sites for the collection of uniform, multi-center data for post processing. In addition, this group will evaluate all MRI studies of the CNS for interval change (i.e. new and enlarging T2 lesion(s), gadolinium enhancement) during follow-up imaging studies and imaging studies acquired during clinical events. At End of Study, changes in T2-lesion volumes, and brain atrophy (SIENA) will be determined.

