5.5 Database fields

The following data will be captured in this study via electronic data capture (EDC).

Clinical Data: Comprehensive demographic data (i.e. date of birth, sex, race and ethnicity, etc.) and clinical data (i.e. date of first clinical visit, reason for the initial MRI scan, findings from the patient's clinical examination (*to include vital signs*), Visual Systems Tests (low vision contrast charts, ocular coherence tomography (OCT)) CMP and CBC results, cerebrospinal fluid test results, new onset clinical attacks, extent of recovery, etc. will be obtained from face-to-face clinical visits and existing medical records. Cognitive/Functional assessments (*EDSS, expanded MSFC (Timed 25-FT Walk (T25-FW), 9-Hole Peg Test (9-HPT), Paced Auditory Serial Addition Test (PASAT-3 (3-second interval pause)), Symbol Digit Modalities Test (SDMT)*), will also be performed. Please refer to Appendix 1 – Cognitive/Functional Assessments

Patient Reported Surveys: Surveys containing questions related to Demographics, Family History, Lifestyle, Environment, and Environmental Exposure and the Neuro Quality of Life Questionnaire (*Neuro-QOL data*), will be completed by each study participant ; included will be inquiries into previous illnesses, the use of over-the-counter supplements, diet, occupational histories, exposure to vaccinations, etc. Please refer to Appendix 2 – Patient Reported Surveys.

Adverse events as well as concomitant medications will be collected and reported. All data collected for clinical assessments will be submitted via EDC and shared with Biogen. At the time of any patient withdrawing from the trial, an attempt will be made to determine the reason for discontinuation.

Radiological Data: Comprehensive radiological data will be collected from RIS subjects. Data to be incorporated into the study database include the date of the first MRI scan demonstrating anomalies within the brain that are suggestive of MS, number of lesions, lesion location, the presence of contrast enhancing lesions, the number of contrast enhancing lesions, changes observed between MRI studies, etc. In addition, data from the clinical MRI study of the cervical spine obtained at screening or Month 0 and at EOS will be incorporated if completed.

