12.3. Analysis of other variables

To validate the association between incidentally identified anomalies within the CNS that are highly suggestive of MS and seminal demyelinating events, systematically acquired environmental exposure, clinical, and radiological, data will be assimilated in an effort to identify significant risk factors. We will evaluate the time from the initial MRI revealing incidental anomalies to the first demyelinating event (acute or initial symptom resulting in a progressive clinical course) or new MRI focus utilizing Kaplan-Meier survival analyses. Log-rank tests will be used to compare survival data between groups at univariate analysis. Multivariate Bayesian Cox regression models will be created to assess the independent predictive value of demographic characteristics (i.e. sex, ethnicity, age at the time of RIS diagnosis), clinical data (i.e. MS family history, occult neurological examination findings, environmental exposure data, CSF profiles, cognitive performance, etc.), and imaging data (i.e. number of brain MRI lesions, the presence of gadolinium enhancing lesions, geographical distribution of lesions, involvement of the spinal

cord, brain atrophy, etc.) on the time to the first symptomatic event. The association of each covariate with time to the first clinical symptom will be quantified by hazard ratios (HR) along with their 95% confidence intervals (CI). Assessments to determine differences between centers will also be performed with statistical adjustments planned for subsequent analyses depending upon the obtained results. Corrections to co-variables will be made when necessary if baseline differences are detected.

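### The synopsis analyses MRI activity as a yes/no proportion although sections 3.2 and 5.3 define the outcome as a lesion count, and the yes/no scale usually costs substantial power

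*Protocol*

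**What the plan says.** Four places in the protocol describe the MRI outcome or its analysis.

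- **Synopsis, Data analysis, Secondary analyses:** "MRI outcomes (proportion of subjects with gadolinium enhancement and new radiologic activity". On its natural reading this is the share of subjects with any activity.
- **Section 3.2:** "The secondary objectives of this study include the change in the number of new or enlarging T2 lesions", followed by enhancing lesions, T2 volume and atrophy.
- **Section 5.3:** "The secondary outcome measures include the number of new or enlarging T2 lesions, and the change in the number of contrast enhancing lesions", followed by T2-lesion and brain volumes.
- **Section 12.3:** a Kaplan-Meier and log-rank analysis, starting at the initial MRI, of time to a first demyelinating event "or new MRI focus utilizing Kaplan-Meier survival analyses".

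Hypothesis (ii) in section 5.1 is that treatment will "reduce the development of new MRI lesions within the CNS compared to subjects randomized to placebo". The data for a count are provided for. Section 5.2.2 says of the Central Imaging Unit that "this group will evaluate all MRI studies of the CNS for interval change", naming new and enlarging T2 lesions. Section 5.5 puts in the database "the number of contrast enhancing lesions, changes observed between MRI studies".

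**The concern.** The outcome is defined as a number, but the one MRI comparison in the synopsis cuts that number at none versus any. A patient with one new lesion and a patient with ten then score the same. A drug that halves the lesion count moves far fewer patients from any to none than it removes lesions. Section 12.3 does not recover the information, because it stops at the first occurrence, mixes clinical with MRI events and does not start at randomization.

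In a trial of about 90 patients, an analysis that follows the synopsis line would test the MRI effect on the weaker scale although the stronger data are collected. The protocol gives no reason for the cut.

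**Working it through.** **The plan's own figure.** There is none to reproduce. All power figures in section 12.1 concern the primary time-to-event endpoint.

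**Inputs from the protocol**
- Section 5.3: "approximately 90 RIS subjects (refer to section 12 for sample size justification) will be treated with either Tecfidera or placebo (1:1 randomization", so n = 45 per arm. The power table in section 12.1 uses 40.
- Effect sizes borrowed from section 12.1: 0.50, the merged-trial 0.58 and the diluted 0.70. They are hazard ratios for clinical events. Using them as lesion rate ratios is an assumption.

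**Inputs assumed because the protocol gives none**
- Two-sided alpha 0.05.
- Placebo mean m of 0.25 to 5 new or enlarging T2 lesions per patient.
- Negative binomial counts with size k, where dispersion = 1/k, so a small k means heavy overdispersion.
- Equal follow-up and no dropout.

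**Formulas**
1. Probability of any lesion: p = 1 − (1 + m/k)^(−k).
2. Yes/no power (pooled two-proportion z test): Φ[(p1 − p2 − 1.96·SE0)/SE1], with SE0 = √(2·p̄(1 − p̄)/n) and SE1 = √([p1(1 − p1) + p2(1 − p2)]/n).
3. Count power (negative binomial): Φ[|ln RR|/SE − 1.96], with SE = √([1/m1 + 1/m2 + 2/k]/n).

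**Mean 1, k = 1, RR 0.50**
- p1 = 0.500, p2 = 0.333, SE0 = 0.1039, SE1 = 0.1024. Yes/no power = Φ[(0.1667 − 0.2037)/0.1024] = Φ(−0.36) = 36%.
- SE = √([1 + 2 + 2]/45) = 0.333. Count power = Φ(0.693/0.333 − 1.96) = Φ(0.12) = 55%.

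**Mean 3, k = 1, RR 0.50**
- p1 = 0.750, p2 = 0.600, SE0 = 0.0987, SE1 = 0.0975. Yes/no power = Φ[(0.150 − 0.1935)/0.0975] = Φ(−0.45) = 33%.
- SE = √([0.333 + 0.667 + 2]/45) = 0.258. Count power = Φ(0.693/0.258 − 1.96) = Φ(0.72) = 77%.

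**Simulation** (2,000 trials per setting, negative binomial likelihood-ratio test, RR 0.50, 45 per arm; null rejection 4.2–6.1% for negative binomial, 3.8–5.6% for Wilcoxon, 4.3–5.7% for yes/no)

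| Placebo mean | Loss of yes/no against negative binomial, over dispersions tried | Example |
|---|---|---|
| 0.25 | 0–4 points | – |
| 0.5 | 5–9 points | – |
| 1 | 12–21 points | k = 0.25: 15% vs 27%; k = 1: 36% vs 57% |
| 2 | 19–36 points | k = 1: 36% vs 72% |
| 3 | 22–46 points | k = 1: 33% vs 76% |

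With 40 per arm and mean 1 the loss is 12–18 points.

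**Where the loss is small**
- RR 0.70, mean 1: 4.1 points (k = 0.25), 5.4 (k = 0.5), 8.4 (k = 1), 10.5 (k = 2). Formulas 2 and 3 also give 4.1 at k = 0.25 (7.0% vs 11.1%), and a separate simulation gave about 2.
- Wilcoxon instead of negative binomial, RR 0.50, mean 1: 1.9 points (k = 0.25), 6.1 (k = 0.5), 10–14 (k of 1 or more).

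**Follow-up.** Treatment runs 3 years or until 31 March 2021 (section 5.3), and last patient in is 30 September 2019 (section 13). That is 548 days, or about 78 weeks, for the last patient, against 144 weeks for a full course. Observation time can therefore differ almost twofold, which affects a yes/no outcome as well as an unadjusted count.

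**The case against.** The strongest case against is that the protocol does not commit to the cut. Sections 3.2 and 5.3 keep the counts as secondary outcomes, and only their statistical method is unstated, which may properly sit in a statistical analysis plan that is not shown. The synopsis line is a parenthesis that names no test and does not claim to be exclusive. It could even be read so that the proportion applies to gadolinium enhancement only. Hypothesis (ii) does not say number, and a proportion developing new lesions would also address it.

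Much of this stands. A reader might infer that the proportion is the only MRI analysis in the protocol, or that the lesion counts are thrown away. Neither is supported: section 12.3 has a further analysis using MRI, and 3.2 and 5.3 retain the counts. Nor do the documents say that hypothesis (ii) will be tested through the synopsis line. A reader might also infer a large power loss whenever lesions average one or more. That is too strong, since at a rate ratio of 0.70, which matches the protocol's own diluted scenario, the loss can be 2 to 4 points.

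What the objection leaves standing is the mismatch. An analysis plan that follows the synopsis inherits the weaker scale, and one that uses counts departs from it. Either way the line needs changing.

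**Conclusion.** The point holds in a limited form. The synopsis states a proportion where 3.2 and 5.3 state a number, and the section 12.3 analysis is also first-occurrence. With 45 per arm, a rate ratio of 0.50 and a placebo mean of 1 or more, the yes/no test gives up about 12 points of power or more against a negative binomial analysis at every dispersion tried.

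This size is conditional on lesion rate, dispersion and effect, none of which the protocol gives for MRI. It also rests on data generated from the model that the count test fits, with equal follow-up and no dropout. The loss falls to about 5 points or less with sparse lesions (mean near 0.25), with a weak effect and heavy overdispersion, or with a rank test under very heavy overdispersion. The case therefore concerns new or enlarging T2 lesions and not enhancing lesions, if few patients enhance. The change is worth making because it is cheap and removes an inconsistency.

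**What to change.** Replace the synopsis line so that it matches 3.2 and 5.3, for example:

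*New or enlarging T2 lesions will be compared between randomized arms as counts, using negative binomial regression with the log of follow-up (scan interval) time as offset. The rate ratio will be given with its 95% CI and a likelihood-ratio or permutation p-value. A rank-based test is the sensitivity analysis. The proportion with any new or enlarging T2 lesion is supportive. Gadolinium enhancement will be compared as a proportion.*

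The cost is wording only, with no extra scans, patients or readings. The downside is some dependence on the model. A moment-based Wald test of the rate ratio rejected up to about 7–8% under the null at high dispersion. The likelihood-ratio or permutation p-value and the rank test guard against this.
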